14.4.2 Toxicity analysis

The analyses of treatment toxicity will be done primarily by tabulation of the incidence of adverse effects with CTCAE grade 2 or more (appendix D). This is done for all patients together for the first 15 cycles and in the following period for all patients together and also separately for MRD positive patients, for patients randomized to arm A and for patients randomized to arm B.

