Secondary objectives (Arm B group)

- Time to and number of patients reinitiating treatment,
- Time to treatment failure after reinitiated treatment.

7 Study design

This study is designed as a phase 2 study with a late randomization in patients MRD negative after cycle 12 and 15, no formal comparisons between the two randomized treatment arms will be made.

During the treatment period all patients receive 15 cycles (28 days each) of oral ibrutinib + venetoclax treatment. During the first 2 cycles, only ibrutinib 420 mg a day is administered. From day 1 in cycle 3, ramp up over five weeks of venetoclax from 20 mg per day to the target of 400 mg per day is administered.

Patients achieving MRD negativity after cycle 12 in peripheral blood (PB) and at day 15 of cycle 15 in PB and bone marrow (BM) are randomized 1:2 between continuous ibrutinib treatment until toxicity or progression (arm A) and treatment free observation (arm B). Patients not reaching MRD negativity after cycle 12 and/or at day 15 of cycle 15 continue ibrutinib treatment until toxicity or progression (non-randomized patients).

MRD negative patients will be closely monitored for relapse/progression during the first 3 years after randomization by means of rapid reporting as described in section 16.1.1.

Patients becoming MRD positive (defined as $MRD \geq 10^{-3}$ and at least one month later $MRD \geq 10^{-2}$), or have symptomatic CLL according to IWCLL criteria (appendix A) during the observation period reinitiate treatment with both ibrutinib and venetoclax for 12 cycles and continue ibrutinib treatment until toxicity or progression.

Patients failing on reinitiating therapy (not reaching any response (CR/PR/SD) according to IWCLL criteria as assessed by the local investigator after 3 cycles of reinitiated therapy (or after reinitiation therapy until 12 months after randomization if progression occurred within 9 months from randomization) are considered as having progressive disease and will go off protocol treatment.

Details of all treatments (dose and schedule) are given in section 9.

8 Study population

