9.4 Reinitiation of therapy for patients randomized to arm B

Patients randomized to Arm B will get reinitiation of therapy during the observation period in case of:

- progression according to IWCLL criteria or
- $MRD \geq 10^{-3}$ (PB) and at least one month later $MRD \geq 10^{-2}$ (PB).

Treatment reinitiation will be as follows:

Venetoclax ramp up as outlined below for cycle 1, day 1 until day 28 after reinitiation, thereafter 400 mg daily (4 tablets. at 100 mg) until 12 cycles of 28 days (from reinitiation of ibrutinib).

Ibrutinib will be administered as a daily oral dosage of 420 mg (3 x 140mg) starting on day 1 of cycle 1 until:

- 1.) Progressive disease (patients not reaching any response (CR/PR/SD) according to IWCLL criteria as assessed by the local investigator after 3 cycles of reinitiated therapy are considered as progressive disease and will go off protocol treatment)

or

- 2.) unacceptable toxicity, whatever occurs first

The continuous daily administration with a slow dose escalation of venetoclax starts on cycle 1 day 1.

Agent	Dose/day	Route of administration	Cycle	Days
Ibrutinib	420 mg	Orally	1-until progression	1-28
Venetoclax	20 mg	Orally	1	1-7
Venetoclax	50 mg	Orally	1	8-14
Venetoclax	100 mg	Orally	1	15-21
Venetoclax	200 mg	Orally	1	22-28
Venetoclax	400 mg	Orally	2-12	1-28

The same precautions regarding TLS are to be taken as described in section 9.2.1.

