Diarrhea and nausea has been registered as relatively common side effects in previous studies albeit the majority of events being relatively mild (grade 2 or lower). The incidence seems to be higher in single agent studies with reported diarrhea (all grades) in 40% and nausea in 38% of subjects. In contrast, in combination studies the incidence of all grade events to be reported, have been 13% for diarrhea and 12% for nausea.

- Neutropenia

Grade 3 or 4 neutropenia occurred in 41% (98/240) of patients treated with venetoclax in the pivotal previously treated CLL 17p deletion study. Monitor complete blood counts throughout the treatment period. Interrupt dosing or reduce dose for severe neutropenia. Consider supportive measures including antimicrobials for signs of infection and use of growth factors (e.g., G-CSF).

- Immunization

The safety and efficacy of immunization with live or attenuated viral vaccines during or following venetoclax therapy have not been studied. Immunization with live virus vaccines is not recommended during treatment and thereafter until B-cell recovery.

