12.2 Adverse event

12.2.1 Reporting of adverse events

Adverse events will be reported from the first study-related procedure until 30 days following the last dose of any drug from the protocol treatment schedule or until the start of subsequent systemic therapy for the disease under study, if earlier.

Adverse events occurring after 30 days should also be reported if considered at least possibly related to the investigational medicinal product by the investigator.

Adverse events have to be reported on the Adverse Events CRF. Adverse events will be scored according to the NCI Common Terminology Criteria for Adverse Events (CTCAE), version 4.0 (see appendix D).

Pre-existing conditions will be collected on the baseline concomitant diseases CRF, i.e. active (symptomatic) diseases of CTCAE grade ≥ 2 diseases under treatment, chronic diseases and long term effects of past events as present at the time of baseline assessment.

All adverse events have to be reported, **with the exception of:**

- ◆ A pre-existing condition that does not increase in severity; the pre-existing condition should be reported on the baseline concomitant diseases CRF
- ◆ AE's of CTCAE grade 1
- ◆ Abnormal laboratory values that have been recorded as being not clinically significant by the investigator in the source documents
- ◆ Relapse/Progression of the disease under study; complications as a result of disease progression remain reportable adverse events.

AESI must be filled out on a separate CRF.

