14.2 Study population definitions

All main analyses will be according the intention to treat principle i.e. patients will be analyzed according to the treatment arm they were assigned to, regardless of whether they received any of the study treatment or not. However, patients initially registered and/or randomized but considered

ineligible afterwards based on information that should have been available before registration and/or randomization, whichever applicable, will be excluded from the respective analyses.

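### After cycle 15 the arm B toxicity row combines off-treatment observation with retreatment, so it describes the strategy but neither state

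*Protocol*

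**What the plan says.** Protocol section 14.4.2 analyses toxicity "primarily by tabulation of the incidence of adverse effects with CTCAE grade 2 or more". One tabulation covers the whole cohort up to cycle 15. Another covers everything after it, overall and by group: "separately for MRD positive patients, for patients randomized to arm A and for patients randomized to arm B". There are thus two periods, with cycle 15 as the only cut, and after that cut one incidence per group.

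In arm B the second period is not uniform. Under section 9.4, "Patients randomized to Arm B will get reinitiation of therapy during the observation period in case of" IWCLL progression or a two-step rise in MRD. Section 7 says that such patients "reinitiate treatment with both ibrutinib and venetoclax for 12 cycles and continue ibrutinib treatment until toxicity or progression". The section 9.4 schedule places a fresh venetoclax ramp-up in cycle 1 of reinitiation, with the same tumor lysis precautions as before.

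Section 14.2 says of the main analyses that "patients will be analyzed according to the treatment arm they were assigned to". Section 13.2 lists type, frequency and severity of adverse events, and their relationship to study treatment, among the secondary endpoints.

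**The concern.** One crude incidence over all arm B patients covers two opposite exposures: no drug, and the two-drug combination restarted from ramp-up. Retreatment events enter a row that is easily read as the toxicity of observation. At the same time they are divided by all arm B patients, including those never retreated. The row also ignores time at risk, although arm A and the MRD-positive group take ibrutinib until toxicity or progression.

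This matters because sections 3 and 17.4 say that the study especially addresses long-term safety and the outcome upon stopping. Elsewhere the protocol treats retreatment as a phase of its own. It has its own schedule (9.4), its own investigations table (10.2.3) and its own efficacy endpoints (13.2: time to and number reinitiating, and time to failure after reinitiation). The toxicity tabulation does not follow suit.

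**Working it through.** **Denominator.** Section 14.4.2 states no figure, so the planned arm B size comes from section 14.1. For 62 patients, success at 44 or more, P0 = 60% and P1 = 75%, the exact binomial gives one-sided alpha 0.0492 and power 0.812, and 62 is the smallest number meeting both limits. Then 62 × 3/2 = 93, 93/0.45 = 206.7 (rounded up to 207) and 207/0.90 = 230. All agree with the protocol, and nothing here disputes them.

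**Size of the mixing.** The protocol gives neither a restart share nor incidences for the two states. The following are assumptions:
- s, share of arm B that restarts: 10–50% (about 6 to 31 of 62)
- q0, incidence during off-treatment observation: 5–20%
- q1, incidence during retreatment: 40–80%

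With independent events and equal reporting in both states, the single arm B incidence is P = q0 + s × q1 × (1 − q0).

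| s | q0 | q1 | P | P/q0 | P/q1 |
|---|---|---|---|---|---|
| 10% | 5% | 40% | 8.8% | 1.76 | 0.22 |
| 10% | 5% | 80% | 12.6% | 2.52 | 0.16 |
| 10% | 20% | 40% | 23.2% | 1.16 | 0.58 |
| 25% | 10% | 60% | 23.5% | 2.35 | 0.39 |
| 50% | 5% | 80% | 43.0% | 8.60 | 0.54 |
| 50% | 20% | 40% | 36.0% | 1.80 | 0.90 |
| 50% | 20% | 80% | 52.0% | 2.60 | 0.65 |

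Over the grid P runs from 9% to 52%. It is 1.2 to 8.6 times q0 and 0.16 to 0.90 of q1. In the 25% line, split rows would show 10% among 62 patients and 60% among about 16, where the specified row shows 23.5%.

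**The parts cannot be recovered.** Solving for q1 gives q1 = (P − q0)/(s × (1 − q0)). With P = 25% and s = 25%:
- q0 = 5% gives 0.20/(0.25 × 0.95) = 84%
- q0 = 20% gives 0.05/(0.25 × 0.80) = 25%

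Knowing the number reinitiated, which the interim reports give, therefore does not separate the two states.

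**Direction.** Equal reporting is not what the protocol sets up. Section 12.2.1 requires adverse events to be reported "until 30 days following the last dose of any drug from the protocol treatment schedule", and later ones only if at least possibly related. During retreatment patients are on protocol drug and full reporting applies. Table 10.2.1 nevertheless marks adverse events at follow-up visits, and section 12.2.1 does not say how its window runs for an arm B patient who may restart. Off-treatment capture is therefore unclear.

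Let f be the fraction of off-treatment incidence that is captured. The recorded row falls below the true q0 when f < (q0 − s × q1)/(q0 × (1 − s × q1)).
- For q0 = 20%, q1 = 40%, s = 10%, the threshold is 0.16/(0.20 × 0.96) = 0.83. Capture below 83% makes the row understate off-treatment toxicity.
- For q0 = 10%, q1 = 60%, s = 25%, s × q1 = 15% already exceeds q0, so the row overstates it at any f.

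Both directions are possible within the assumed ranges.

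**The case against.** The strongest reply is that arm B is a strategy: stop, then restart on defined triggers. Incidence by assigned arm summarizes that strategy correctly and agrees with section 14.2. It misleads only a reader who takes it for off-drug toxicity, which section 14.4.2 never claims. No formal comparison between arms is planned (sections 7 and 14), so no test is affected. The word primarily in 14.4.2 leaves room for further tables, and section 14.4.6 defers detail to a SAP that is not at hand.

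Most of this stands. The by-arm row is valid and should stay. But 14.4.2 is not silent: it fixes the periods and the rows. Room to add a split is not a commitment to one.

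Three stronger readings are tempting, and the documents do not support them.
- A reader might infer that the table overstates the toxicity of stopping. The reporting window makes the direction uncertain, as shown above.
- A reader might infer that retreatment safety goes unreported. Every tumor lysis case is an SAE (12.1, 12.3.1), the DSMB receives annual adverse event listings (12.9), and the post-randomization interim reports cover the number reinitiated and events of special interest (14.4.4). What is missing is a separate incidence for retreatment in the specified tabulation.
- A reader might take the statement in section 9.7.1 that "Grade 3 or 4 neutropenia occurred in 41% (98/240) of patients treated with venetoclax" as the retreatment rate and work out a dilution from it. That figure comes from a previously treated 17p-deletion study and concerns grade 3 or 4 events, while the table counts grade 2 or more. The same section gives 36.0% for grade 3 and above across the CLL/SLL monotherapy studies. Neither figure is a retreatment rate for patients who were MRD negative at randomization.

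**Conclusion.** The point holds as one of tabulation. After cycle 15 the specified arm B row describes the stop-then-retreat strategy and cannot show the toxicity of observation or of retreatment, although safety in relation to treatment is a secondary endpoint. The direction of any distortion is uncertain, and its size cannot be derived from the documents. The ranges of 1.2 to 8.6 times the off-treatment incidence and 0.16 to 0.90 of the retreatment incidence rest on the assumed restart share and incidences, on independence and on equal reporting. They show that the mixing can be large, not how large it will be. The primary endpoint, the sample size and every treatment rule are untouched.

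**What to change.** In section 14.4.2 keep the by-arm row, labeled as the summary of the assigned strategy, and add two rows for arm B:
1. Off-treatment observation, ending at reinitiation.
2. Reinitiated treatment, restarters only, with the ramp-up cycle (cycle 1 in section 9.4) shown separately.

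For each give the number at risk, patients with an event and patient-time. Give patient-time for arm A and the MRD-positive group as well.

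Footnote the section 12.2.1 reporting window and state how it applies during arm B observation. Do not compare off-treatment rates per patient-year with the on-treatment groups unless both are restricted to events captured equally, such as those at least possibly related. Otherwise the split brings in a bias of its own. Note too that restarters are selected by relapse or MRD rise, so row 2 is descriptive.

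The cost is a paragraph of wording and some programming. Treatment timing is on the CRF (section 16.1). Onset dates of adverse events are not listed there, but 14.4.2 already divides events at cycle 15, so they must be datable; confirm that this also serves a cut at reinitiation. The retreatment row will be small and imprecise.

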14.4.3 Additional analyses

Additional analyses regarding secondary endpoints will involve progression-free survival (PFS), overall survival (OS), and overall response rate. These analyses should also be regarded as exploratory, and therefore only as hypothesis-generating. .

14.4.4 Interim analysis

No interim analysis on the primary endpoint is planned.

Draft outline of interim analyses in the study:

Analysis	Time point	Analysis	Impact on primary endpoint
Analysis IA	First 15 pt. after induction cycle 3	Interim analysis on safety	No, only safety
Analysis IB	First 10 pt. with low CrCl 30-50. After induction cycle 3.	Interim analysis on safety	No, only safety
Analysis II	first 23 pt. reaching MRD negativity at cycle 9 or first 51 pt. at cycle 9, which occurs first	Interim analysis on safety and efficacy	No impact, prior to randomization
Analysis III	15 pt. randomized for stopping treatment after cycle 15 or first 51 pt. at end of cycle15, which	Interim analysis on safety and efficacy	No impact, at time of randomization

	occurs first		
Analysis IV	6 months after first 15 pt. randomized for stopping treatment at cycle 15 or 6 months after first 51 pt. at cycle 15, which occurs first	Interim analysis on efficacy	Post randomization, MRD positivity and primary are dependent. No correction.
Analysis V	12 months after 15 pt. randomized for stopping treatment at cycle 15 or 12 months after first 51 pt. at cycle 15, which occurs first	Interim analysis on efficacy	Post randomization, MRD positivity and primary are dependent. No correction
Analysis VI	Last patient reaching Month 27	Primary end point analysis	
Analysis VII	Last patient reaching 7 years	Update final analysis	

In the Interim analyses on safety (IA and IB), , the incidence of (serious) adverse events, death, creatinine level, AEs of special interest (atrial fibrillation, bleeding events and TLS) and progression according to appendix B and MRD positivity, will be reported. These analyses will be before the randomization stage and patients have not been assigned to any of the arms.

In Interim analysis on safety and efficacy and In Interim analysis on efficacy, the incidence of (serious) adverse events, death, creatinine level, number of assigned patients at each treatment arm, number of progression, best response, number of reinitiated patients (if applicable), AEs of special interest (atrial fibrillation and bleeding events), TLS)and progression according to appendix B and MRD positivity, will be reported.

In Interim analyses on efficacy (IV, V), the number of assigned patients at each treatment arm, number of progression, best response, number of reinitiated patients (if applicable), AEs of special interest and progression according to appendix B and MRD positivity, will be reported.

All aforementioned analyses will be reported to the DSMB

14.4.5 Statistical analysis of the quality of life assessment (QoL)

All patients with at least the baseline QoL and one treatment or follow-up QoL questionnaire will be included in this analysis. QoL at the different time points will be summarized (median, range, number of patients); measurements during treatment and follow up will be compared to the corresponding baseline values, and the differences compared to baseline will be analyzed using a one-sample t-test. Time series analysis will be performed. To obtain estimates of the mean scores for the EORTC QLQC30 and QLQ-CLL16 subscales a linear mixed model will be used. The subscales that are based on a single item will be analyzed using (ordinal) logistic regression. More details of the analysis will be described in a statistical analysis plan (SAP) which will be made prior to the final analysis of the quality of life. Next to time, other covariates will be included in a multivariate model such as toxicity and last registered response (e.g., \geq PR vs. $<$ PR) prior to a certain HRQoL assessment.

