9.1 Treatment with ibrutinib and venetoclax

All patients should start protocol treatment (cycle 1, day 1), within 28 days after registration, or in case of new uncontrolled infection occurring after registration, when infection is under control.

All patients receive 15 cycles of ibrutinib + venetoclax (with ramp up and delayed start, see below). Each cycle has a duration of 28 days.

After 15 cycles of ibrutinib + venetoclax, subsequent treatment will be based on MRD status:

- Patients not achieving MRD negativity after cycle 12 (PB) AND/OR at day 15 of cycle 15 (PB+BM) continue on ibrutinib maintenance (non-randomized patients)
- Patients achieving MRD negativity after cycle 12 (PB) AND at day 15 of cycle 15 (PB+BM) are randomized 1:2 between ibrutinib maintenance (Arm A) and stopping treatment (observation) (Arm B).

Ibrutinib will be administered as a daily oral dosage of 420 mg (3 x 140 mg) starting on day 1 of cycle 1.

Venetoclax administration starts in cycle 3. Assessment of subject-specific factors for level of risk of TLS and providing prophylactic hydration and anti-hyperuricemics to subjects prior to first dose of venetoclax to reduce risk of TLS is mandatory (see appendix G). Venetoclax will be administered orally once daily beginning with a dose ramp-up period. The initial venetoclax dose is 20 mg. After one week of treatment at 20 mg, the dose will be escalated to 50 mg, followed by subsequent increases, each after one week, to 100 mg, 200 mg and the maximum dose of 400 mg. The 5-week ramp-up dosing schedule is designed to gradually reduce tumor burden (debulk) and decrease the risk of TLS.

Patients with a high tumor burden or assessed as high risk for TLS at baseline, should be re-assessed for TLS risk, at the end of cycle 2 (before venetoclax ramp up) including a CT-scan,

absolute leucocyte count (ALC) and creatinine clearance (CrCl, directly measured with 24hr urine collection or calculated according to the modified formula of Cockcroft and Gault, appendix E).

For patients with CrCL between 30-50 ml/min , inclusion in the trial is acceptable if:

- ◆ CrCl and ALC count will be re-assessed at end of cycle 2 (before venetoclax ramp up)
- ◆ Upon significant (above 15%) creatinine increase, treatment will be put on hold for a work up by a nephrologist to assess whether treatment can be reinitiated
- ◆ Re-assessment with a CT scan will be performed at end of cycle 2
(using contrast is up to local investigator based on kidney function)

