10.2 Required investigations

Table 10.2.1 Required investigations at entry, during treatment and during follow up

	At entry ¹	After each induction cycle	Extra at end of cycle 2	Cycle 3 day 8 and 15 Cycle 4 day1	Extra at end of cycle 3 and 6	Extra at end of cycle 9	Extra at end of cycle 12	Extra at day 15 of cycle 15 ⁹	After cycle 15: Every 3 months for 2 years, every 4 months for 3 rd year (= until 51 months)	Extra at month 27	After month 51 ²	Progressive disease
Informed consent	X											
Medical history	X											
Adverse events	X	X							X		X	
Physical examination	X	X							X		X	X
CIRS / CCI	X											
Rapid Report Form					X	X	X					
Binet stage	X											
TLS risk category (appendix G)	X		X ⁴									
Lab tests												
Hematology	X	X							X		X	X
Blood chemistry	X	X							X		X	
Additional chemistry	X											
Virology	X											
Bone marrow												
Bone marrow biopsy								X		X		X
(PET)-CT scan ⁵	X		X ⁶					X		X		X
(Clinical) response evaluation					X ⁷	X	X		X	X	X	X
Quality of Life ⁷	X								X ⁸		X ⁸	
Pregnancy test	X											

- Laboratory tests should be performed within 2 weeks prior to registration flow and CT can be maximally 42 days old
- Every 6 months until 7 years after registration or until progression, whatever comes first.
- The form needs to be filled out every 3 months for as long as the patient is on ibrutinib treatment
- In patients with high risk for TLS or CrCL 30-50 ml/min
- PET only in case of suspected transformation.
- CT scan after cycle 2 in patients with high risk for TLS or CrCL 30-50 ml/min
- Only at end of cycle 3
- Quality of life at entry, after induction cycle 15 and at 6 months, 1, 2 and 3 years after start maintenance/observation.

9. MRD and CT should be done at day 15 cycle 15 to have results available to assess SD, PR, CR, MRD negativity at end of cycle 15.

Table 10.2.2 .Collection for central lab.

	At entry	After each induction cycle	Extra at end of cycle 2	Cycle 3 day 8 and 15 Cycle 4 day1	Extra at end of cycle 3 and 6	Extra at end of cycle 9	Extra at end of cycle 12	Extra at day 15 of cycle 15 ⁴	After cycle 15: Every 3 months for 2 years, every 4 months for 3 rd year (= until 51 months)	Extra at month 27	After month 51	Progressive disease
Mutational status¹ PB	X											
Serum parameters	X											
FISH/CGH and NGS PB	X											X
MRD (flowcytometry)												
PB	X		X			X	X	X	X ²	X ²		X
BM aspirate								X		X		X
Side studies												
PB	X		X	X		X	X	X	X	X		X

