10.5 Quality of Life assessment

Health related outcome parameters will be collected in this study, i.e. quality of life (QoL).

QoL will be assessed at entry, after 15 induction cycles and at 6 months, 1, 2 and 3 years after start maintenance/ observation.

The quality of life measurements will be continued after the patient is off protocol treatment, but discontinued when progression has been observed.

- EORTC QLQ-C30 questionnaire
- EORTC QLQ-CLL16

Collection of the QoL questionnaires will be performed in the following manner:

A QoL coordinator will be assigned in each participating center. The QoL questionnaire collection is left to the responsibility of the QoL coordinator. As soon as a patient is registered at the HOVON Data Center (HDC) the QoL coordinator is notified by email. Patient study number, (partial) date of birth and date of registration are mentioned in this mail.

The patient will be provided a paper print out of the questionnaire.

The baseline questionnaire will be handed or sent to the patient by the QoL coordinator. At the time points mentioned in the beginning of this section, the coordinator will hand over the questionnaire at the correct date.

The QoL coordinator will collect the questionnaire from the patient and will send them to the HOVON Data Center.

The questionnaires are described in appendix L.

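### The QoL analysis set requires a form after baseline, and none is due until after cycle 15, so usable baseline data are dropped for patients who never supply a later form

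*Protocol*

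**What the plan says.** Section 14.4.5 of the protocol fixes who enters the QoL analysis: "All patients with at least the baseline QoL and one treatment or follow-up QoL questionnaire will be included in this analysis". The rest of the section works on that set. It covers summaries at each time point (median, range, number of patients), tests of change from baseline ("the differences compared to baseline will be analyzed using a one-sample t-test"), and a model for the mean scores ("To obtain estimates of the mean scores for the EORTC QLQC30 and QLQ-CLL16 subscales a linear mixed model will be used"). Single-item scales go to ordinal logistic regression.

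The schedule is in section 10.5: "QoL will be assessed at entry, after 15 induction cycles and at 6 months, 1, 2 and 3 years after start maintenance/ observation". The note to the table of required investigations in section 10.2 gives the same times. Section 10.5 also says when collection ends: "The quality of life measurements will be continued after the patient is off protocol treatment, but discontinued when progression has been observed".

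Section 14.4.5 leaves further detail to a statistical analysis plan, but it states the inclusion rule itself. A plan that follows the protocol would inherit the rule.

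**The concern.** A baseline-plus-one rule does little harm when the next form comes soon after baseline. Here it comes after the whole induction phase. The set is therefore made up of patients who could still supply a form some 14 months later or beyond, yet it is used to describe baseline QoL and change from baseline in a trial where QoL is a secondary objective for all treatment groups.

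The rule is also more restrictive than the planned model needs. A one-sample t-test of differences needs both values, so the rule costs nothing there. A likelihood-based mixed model with baseline among the responses does not need both: a patient with only a baseline form still informs the baseline mean and, through the within-patient correlation, the adjusted later means. Excluding these patients discards observed data that may predict who is lost. It also gives up validity under missing at random given baseline.

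At stake are the reported baseline level and the estimated change from it. The primary endpoint is not affected.

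**Working it through.** **1. Time to the first form after baseline.** Section 9.1: "Each cycle has a duration of 28 days". Section 10.5 and the note in section 10.2 ("Quality of life at entry, after induction cycle 15 and at 6 months, 1, 2 and 3 years") agree that nothing is collected between entry and the end of cycle 15. So 15 x 28 = 420 days = 60 weeks, and 420 / 30.44 = 13.8 months.

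**2. Who is excluded.** Setting 14.4.5 against 10.5, 11.2 and 11.3:

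- Death before the end of cycle 15: no later form, excluded.
- Progression before then: collection stops, excluded.
- Withdrawal of consent for further data collection before then: excluded.
- Alive, progression-free and consenting, but never returns a later form: excluded.
- Misses the cycle 15 form but returns one at 6 months or later: included.
- Stops treatment only (for example for toxicity): collection continues, so the patient can be included. The protocol does not say when forms fall due for a patient who stops before cycle 15, since the time points are tied to cycle 15 and to the start of maintenance or observation.

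**3. Shift in the analysed baseline.** Let q be the share lost, R the baseline mean of those retained, L that of those lost, and D = R - L. The overall mean is (1 - q)R + qL = R - qD, so the retained mean exceeds the overall mean by qD. The protocol gives neither q nor D. The values below are assumed, on an assumed 0-100 scale where higher is better. Counts use the 207 eligible patients of section 14.1.

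| q | Patients (of 207) | D | Baseline shift qD |
|---|---|---|---|
| 10% | 21 | 5 | 0.5 |
| 20% | 41 | 10 | 2.0 |
| 30% | 62 | 15 | 4.5 |

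**4. Shift in the estimated change.** Assume that loss depends only on baseline, that the SD is equal at both times, and that the correlation is r. The retained follow-up mean is then too high by r x qD, so the change is too low by (1 - r) x qD. At q = 20% and D = 10:

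- r = 0.3: 0.7 x 2.0 = 1.4 points
- r = 0.5: 0.5 x 2.0 = 1.0 point
- r = 0.7: 0.3 x 2.0 = 0.6 points

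The mechanism is regression to the mean. Retained patients are selected for a high baseline, so improvement is understated.

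**5. Scale against sampling error.** With SD 20 and r = 0.5 (assumed), the SD of the change is 20 x sqrt(2 x 0.5) = 20. With 207 - 41 = 166 patients, the standard error is 20 / sqrt(166) = 1.6. A 1-point shift is below one standard error.

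**6. Simulation check.** Assumed baseline mean 65, SD 20, correlation 0.5, true change +5, and loss more likely at low baseline scores.

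| Loss | Retained minus lost, baseline | Baseline, restricted set | Change, restricted set | Change, all baseline forms |
|---|---|---|---|---|
| 10% | 18.0 | 66.7 | 4.2 | 5.1 |
| 20% | 17.2 | 68.4 | 3.3 | 5.0 |
| 30% | 16.8 | 70.0 | 2.5 | 5.0 |

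The results follow the formulas: at 20%, 0.2 x 17.2 = 3.4 for baseline and half of that, 1.7, for change. The baseline gap of about 17 points is wider than any in step 3. The table shows that using all baseline forms removes this kind of bias. It does not indicate the size to expect in this trial.

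**The case against.** The strongest reply is that the harm is small and partly conditional.

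- Section 14.4.5 does not say whether baseline is a response or a covariate in the mixed model. If it is a covariate, baseline-only patients add nothing and the rule costs the model nothing. This stands as far as it goes. The loss from the baseline summary remains, and the benefit to the model depends on specifying baseline as a response.
- No attrition rate or baseline gap is documented, and in the central example the effect on change is smaller than its standard error. This stands, and it limits severity.
- Describing patients who have follow-up forms is a legitimate target. It is, but the section does not name that target, and QoL is listed as an objective for all treatment groups.
- Adding baseline-only patients brings no information from induction, and for patients who died the model projects scores that do not exist. Both points stand and are costs of the fix.

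A reader might also infer more than the documents support. One inference is that everyone who leaves treatment during induction is excluded. Section 10.5 continues collection off treatment, and section 11.2 keeps withdrawn patients in follow-up. Another is that induction is the period of greatest loss; the protocol gives no attrition figure for any period. A third is that the rule flatters the treatment. If lost patients had worse baseline QoL, the baseline looks better than it was but improvement is understated. If they had better baseline QoL, both directions reverse.

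**Conclusion.** The concern holds as a minor one. The exclusion follows from the text: 14.4.5 requires a later form, none is due for 420 days, and patients who die, progress, withdraw data consent or return no later form lose a usable baseline record. Because the protocol states the rule, this is not a detail merely left to the analysis plan.

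The size is not known. Under an assumed 20% loss and 10-point gap, the analysed baseline is 2 points too high. At a correlation of 0.5 the change is about 1 point too low. Both figures assume that loss depends on baseline QoL; if it does not, there is no shift, only a loss of precision.

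Section 14.4.6 treats everything except the primary analysis as hypothesis-generating. Nothing here bears on the arm B test, a safety decision or a comparison between arms.

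**What to change.** In section 14.4.5, or in the analysis plan with the deviation recorded:

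- Include every eligible patient with at least one QoL form in the linear mixed model, with baseline as a response and time as categorical.
- Summarise baseline QoL for all eligible patients with a baseline form.
- Report the number and baseline scores of patients without a later form, with deaths counted alongside.
- Keep the one-sample t-tests as descriptive results in patients with both forms.

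The cost is wording and one extra table, with no new data. Section 14.4.6 allows such changes outside the primary analysis. The model would rely on missing at random given baseline. It would not repair loss driven by unobserved QoL during induction, and it would implicitly project QoL for patients who died, which is why deaths should be shown next to the estimates.
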